- ^e All subjects will be tested to assess *CFTR* genotype, regardless of availability of a previous *CFTR* genotype laboratory report. Refer to Section 11.6.2 for details. However, this assessment does not need to be repeated for confirmed subjects in Part A who may participate in Part B.
- f Refer to Section 11.6.2 for details.
- If an eligible historical sweat chloride result is documented in the subject's medical record, that result alone (and not the Screening Visit result) may be used to determine eligibility. For subjects using an historical sweat chloride value documented in their medical record to determine eligibility, the sweat chloride test at the Screening Visit is still required. At screening, 2 samples may be collected, 1 sample from each arm (left and right).
- h The LCI assessment (subjects ≥3 years of age at screening who consent/assent to the optional LCI Substudy) may be performed pre- or post-bronchodilator. The assessment will be performed in multiple replicates and before the spirometry assessment. Refer to Section 11.4.2 for details.
- Spirometry (subjects ≥3 years of age at screening only) may be performed pre- or post-bronchodilator. Refer to Section 11.6.7 for details.
- Refer to Section 9.4.2 for details.

Study VX15-809-115: Part B Treatment Period and Safety Follow-up Visit Table 3-4

					Treatment Period	Period					Safety
											Follow-up Visit
										Early	(Week 26
										Termination	[2 weeks
		Day 3								Jo	± 4 days
	Day 1	(±1	Day 15	Week 4	Week 8	Week 12 Week 16 Week 24	Week 16	Week 20	Week 24	Treatment	After Last
Event/Assessment ^a		day)	(± 3 days)	(± 5 days)	(± 5 days)	$(\pm 3 \text{ days}) (\pm 5 \text{ days}) $	(± 5 days)	(± 5 days)	_	(ETT) Visit ^b	Dose])c,d
Clinic visit	X		X	X	X		X		X	X	X
Telephone contact ^e		X				X		X			
Stature and weight ^f	X		X	X	X		X		X	X	X
Vital signs ^g	$X_{ m p}$		X	X	X		X		X	X	X
Pulse oximetry ^g	X		X	X	X		X		X	X	X
Ophthalmologic examination								×	X^{i}	Xį	X^{i}

- All assessments will be performed before LUMIVA dosing unless noted otherwise (Section 11.1). When repeats of an assessment are required postdose at a given visit, the assessment will be collected only once if LUM/IVA is not administered on the day of the visit (i.e., LUM/IVA interruption or permanent LUM/IVA

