 - Samples will be collected at the study center during the study visit; however, samples may be collected by the subject's caregiver up to 24 hours before the study visit (e.g., at home) and brought to the study visit (Section 11.4.5). The sample may be collected pre- or postdose.
 - The sweat chloride test must be conducted predose relative to the morning dose of LUM/IVA during the Treatment Period (at approximately the same time as predose blood collections). At each time point, 2 samples will be collected, 1 sample from each arm (left and right). Refer to Section 11.4.1 for details.

Study VX15-809-115: Part B Treatment Period and Safety Follow-up Visit Table 3-4

					Treatment Period	Period					Safety
											Follow-up Visit
										Early	(Week 26
										Termination	2 weeks
		Day 3								Jo	± 4 days
	Day 1	(± 1	Day 15	Week 4	Week 8	Week 12	Week 12 Week 16 Week 20 Week 24	Week 20	Week 24	Treatment	After Last
Event/Assessment ^a		day)	(± 3 days)	_	(± 5 days) (± 5 days)		$(\pm 5 \text{ days})$ $(\pm 5 \text{ days})$ $(\pm 5 \text{ days})$ $(\pm 5 \text{ days})$	(± 5 days)	(± 5 days)	(ETT) Visit ^b	Dose])c,d
LCI (optional) ^{\$}	X			X					X	X	X
Spirometry ^t	$_{ m n}X$		X	X	X		X		X	X	X
Other events related to	X		X	X	X	X	X	X	X	X	
outcome											
LUM/IVA dosing ^w					LUM/IVA q12h	q12h					
Observation 4 hours after the	X										
first dose											
Acceptability/palatability	X										
assessment ^x											
Study drug count			X	X	X		X		X	X	
Medications, treatments, and				Continuou	s from signin	Continuous from signing of ICF through Safety Follow-up Visit (if required)	ough Safety l	Follow-up V	isit (if requir	(pa.	
procedures review ^y											
Adverse events				Continuou	s from signin	Continuous from signing of ICF through Safety Follow-up Visit (if required)	ough Safety l	Follow-up V	isit (if requir	(pa.	
AD. Advance second. D.M. Lade mane indem CD. correla Chancie. DCCs abstractualisments DTF. Dust's Townsiantian of Transferment ICD. informed account from	000000	law CE.	orretio Ghraci	C. DCG. alas	tecondiage	PTT. Basi	L. Tommingti	Tanton	ant. ICE. int	Gamed concent	Commit

AE: adverse event; BMI: body mass index; CF: cystic fibrosis; ECG: electrocardiogram; ETT: Early Termination of Treatment; ICF: informed consent form; IVA: ivacaftor; LCI: lung clearance index; LUM: lumacaftor; PK: pharmacokinetic; q12h: every 12 hours

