11 ASSESSMENTS

11.1 Timing of Assessments

The timing of assessments is shown in:

- Table 3-1 and Table 3-2 for Part A, and
- Table 3-3 and Table 3-4 for Part B.

The following assessments must be performed in the order specified below when more than 1 assessment is required at a particular time point:

- 1. Predose ECGs and vital signs should be performed before any other procedures that may affect heart rate (e.g., blood draws including PK).
- 2. PK sampling and spirometry may be performed in either order.
- 3. For Part B only, the LCI assessment (if applicable) should be performed before spirometry.
- 4. For Part B only, the FE-1 sample may be collected at the study center during the study visit or may be collected by the subject up to 24 hours before the study visit at home and brought to the study visit. The sample may be collected pre- or postdose.

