11.4 Pharmacodynamics

Part A

Not applicable.

Part B

The PD assessments described in Section 11.4.1 through Section 11.4.9 will be performed in Part B.

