11.4.5 Fecal Elastase-1

Stool samples for assessment of FE-1 will be collected at the time points noted in Table 3-4. Samples will be collected at the study center during the study visit; however, samples may be collected by the subject's caregiver up to 24 hours before the study visit (e.g., at home) and brought to the study visit. Specific instructions for the collection, processing, and shipment of samples will be provided in a separate laboratory manual.

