12.3.1 General Considerations

This section applies to Part A and Part B, unless otherwise specified.

For Part A and Part B, all individual subject data based on All Subjects Set of the corresponding part will be presented in data listings.

Continuous variables will be summarized using the following descriptive summary statistics: number of subjects (n), mean, SD, standard error (SE), median, minimum, and maximum.

Categorical variables will be summarized using counts and percentages.

Baseline value: For Part A and Part B, unless otherwise specified, the baseline value will be defined as the most recent non-missing measurement (scheduled or unscheduled) collected before the initial administration of study drug.

• For ECG, the baseline will be defined as the average of the 3 pretreatment measurements on Day 1.

For Part B only:

- For LCI-related parameters, the values at each visit will be calculated from the technically acceptable washout replicates as detailed in Section 12.3.3.2.12. The baseline of LCI will be the most recent non-missing value calculated from the technically acceptable replicates before the initial administration of study drug.
- For sweat chloride, the values at each visit will be based on the averaged measurements from left and right arms as specified in Section 12.3.3.2.1. The baseline will be defined as the average of the values at screening and the pretreatment measurement on Day 1. If only 1 pre-first dose measurement of sweat chloride is available, that measurement will be considered the baseline.

Change (absolute change) from baseline: will be calculated as postbaseline value - baseline value.

Relative change from baseline: will be calculated and presented in percentage as $100 \times (postbaseline \ value - baseline \ value)/baseline \ value$.

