12.3.3.2.5 Analysis of Pulmonary Exacerbation-related Other Secondary Pharmacodynamic Variables

- Time-to-first pulmonary exacerbation through Week 24: Time-to-first pulmonary exacerbation will be analyzed using Kaplan-Meier method. Cumulative incidence of pulmonary exacerbation will be summarized and plotted. Subjects without an exacerbation by Week 24 Visit will be censored at Week 24 Visit or at the last visit before the Safety Follow-up Visit for subjects with missing Week 24 Visit.
- Number of pulmonary exacerbations through Week 24: The number of pulmonary exacerbations through Week 24 [inclusive] (including both on-treatment events and events after treatment discontinuation), normalized by the time spent in the study (Week 24 date first dose date +1), will be summarized.
- Number of CF-related hospitalizations through Week 24: For the number of CF-related hospitalizations through Week 24 [inclusive], the analysis will be similar to the analysis of the number of pulmonary exacerbations through Week 24.

12.3.3.2.6 Absolute Change in FE-1 Levels From Baseline at Week 24

Descriptive summary statistics (n, mean, SD, SE, median, minimum, and maximum), along with 95% confidence interval and within-group *P* values based on Normal approximation, will be provided for absolute change from baseline in FE-1 levels at Week 24. In addition, descriptive summary statistics, along with 95% confidence interval based on Normal approximation, will be provided at all other visits.

Number and percentage of subjects with pancreatic insufficiency, defined as having FE-1 level $<200 \mu g/g$, will be provided at Week 24 and at baseline. The within-group shift will be tested based on McNemar's test.

12.3.3.2.7 Absolute Change in Serum Levels of IRT From Baseline Through Week 24

For each subject, the serum levels of IRT through Week 24 for each subject will be derived as the simple arithmetic mean at each visit (Day 15, Weeks 4, 8, 16, and 24), regardless of on-treatment measurement or measurement after treatment discontinuation. As long as there is at least 1 measurement available, the average will be calculated based on all available measurements. If all measurements are missing, then the average through Week 24 will be missing and the subject will not be included in the summary for the average through Week 24. The absolute change in serum levels of IRT from baseline through Week 24 will be

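### The Day 1 FE-1 sample may be taken after the first dose, but the stated baseline must precede it, so a child with no predose stool has no FE-1 baseline unless the SAP provides one

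*Protocol*

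**What the plan says.** **Schedule.** Section 11.4.5 states: "Stool samples for assessment of FE-1 will be collected at the time points noted in Table 3-4". The first of those time points is Day 1. The Part B screening schedule (Table 3-3) has no FE-1 row. FE-1 is a pharmacodynamic assessment, and Section 11.4 lists none for Part A, so no earlier study sample is planned.

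**Collection rule.** The general footnote to Table 3-4 places assessments before dosing unless an exception is noted. The FE-1 footnote is such an exception: "The sample may be collected pre- or postdose". Section 11.1 item 4 says the same. Both, with Section 11.4.5, also let the stool be collected at home in the 24 hours before the visit.

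**Baseline rule.** Section 12.3.1 defines baseline, unless otherwise specified, as "the most recent non-missing measurement (scheduled or unscheduled) collected before the initial administration of study drug". It then sets separate rules for ECG, LCI and sweat chloride, but none for FE-1.

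**Analyses that use the baseline.** Section 12.3.3.2.6 gives the FE-1 change at Week 24 with a 95% confidence interval and a within-group P value, and the change at other visits with a confidence interval. The number and percentage of children below 200 µg/g "will be provided at Week 24 and at baseline. The within-group shift will be tested based on McNemar's test".

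**The concern.** The collection rule and the baseline rule do not fit together at Day 1. A site can follow the schedule exactly and still obtain a Day 1 value that the baseline definition cannot use. Because this would not be a deviation, nothing would flag it while the trial runs.

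At later visits the freedom to sample before or after dosing does no harm, and at Week 24 it makes no difference because no morning dose is given. Day 1 is the only visit at which the order of stool and dose decides whether the value can serve its purpose, and it is not singled out.

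At stake are the FE-1 changes at every visit and the paired shift in pancreatic insufficiency, in a small single-arm study. Section 8.3.3 states a hypothesis for this endpoint, namely that FE-1 rises if pancreatic function is rescued.

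**Working it through.** This is mainly a comparison of text.

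1. *Is there a scheduled FE-1 sample before Day 1?* No. Table 3-3 has no FE-1 row and Part A has no pharmacodynamic sampling.
2. *May the Day 1 sample follow the first dose?* Yes, under the Table 3-4 footnote and Section 11.1 item 4.
3. *Can a postdose Day 1 value be the baseline?* Not under Section 12.3.1 as written. Unscheduled predose values would count, but none is planned for FE-1.
4. *Which children are exposed?* The first dose is given at the site on Day 1, so a home sample from the preceding 24 hours is predose and qualifies. So does a clinic sample taken before dosing. Only a child with neither is exposed.
5. *What is lost for that child?* Change is the postbaseline value minus the baseline value, so with no baseline it cannot be computed at any visit. McNemar's test needs a baseline and Week 24 pair, so the child leaves that test too.

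Sweat chloride shows the contrast. It has a screening sample, must be taken before the morning dose during treatment, and has a stated rule for when only one pre-first-dose value exists. FE-1 has none of the three.

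**The plan's own figures.** The protocol gives no precision or sample-size figure for FE-1. Its only sample-size figures, in Section 12.1, reproduce:
- At least one subject with an adverse event among 50: 1 − 0.95^50 = 92.31% (stated 92.3%) and 1 − 0.90^50 = 99.48% (stated 99.5%).
- Completers: 56 × 0.9 = 50.4, about 50.

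**Illustration of size.** The documents do not say what share of Day 1 samples would be postdose, so the share p is an assumption. With n children otherwise evaluable, n(1 − p) remain, and with the same SD the interval width is multiplied by √(n / [n(1 − p)]) = 1/√(1 − p). This factor does not depend on n. Counts are shown for the 50 expected completers and for the roughly 56 in the Full Analysis Set, on which pharmacodynamic analyses other than LCI are based.

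| Assumed p | Left of 50 | Left of 56 | Width factor |
|---|---|---|---|
| 10% | 45 | 50.4 | 1/√0.90 = 1.05 |
| 20% | 40 | 44.8 | 1/√0.80 = 1.12 |
| 30% | 35 | 39.2 | 1/√0.70 = 1.20 |
| 50% | 25 | 28 | 1/√0.50 = 1.41 |

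**The case against.** **The SAP may settle it.** The baseline definition applies unless otherwise specified, and Sections 12 and 12.3 leave analysis detail to a Part B SAP finalized before the data cut or lock. A rule there admitting a Day 1 postdose value would be planned, not post hoc. This stands in part. A reader might infer that these children are certain to drop out of every FE-1 analysis, or that only an unplanned decision could keep them; the documents do not support either inference, because the SAP is not shown. What the SAP cannot do is recover a predose sample that was never taken. It could only widen the definition of baseline.

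**Home collection already answers the practical difficulty.** The 24-hour window lets a caregiver bring a predose stool to Day 1. This stands, and it limits the problem to children with neither kind of predose sample.

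**Postdose collection may be rare.** A reader might infer that it would be common, since young children do not pass stool on demand and each child is observed for 4 hours after the first dose. The documents do not link that observation period to stool collection and give no frequency. The assumed shares are illustrative, and the upper end would need half of the children to have no predose sample at all.

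**A fallback that accepts a postdose value shows the harm is modest.** This is fair: such a rule would keep these children in the analysis. It is still second best, because the documents do not say whether a stool passed shortly after the first dose can stand for the pretreatment state. A predose sample avoids the question.

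**The stakes are low.** This stands. FE-1 is one of many secondary endpoints, analyzed within group without a control, and no formal sample size calculation was performed.

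**Conclusion.** The mismatch is real and can be read directly from the protocol: at Day 1 it allows a sample that its own baseline definition cannot use, with no other scheduled pretreatment sample and no FE-1-specific rule. A child without a home sample from the prior 24 hours or a predose clinic sample would have no FE-1 baseline, and would be missing from the change summaries and the shift test, unless the SAP specifies otherwise.

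The textual conflict is certain; the amount of data lost is not. It may be small. The range of 1.05 to 1.41 in interval width rests wholly on an assumed 10% to 50% affected and an unchanged SD. The point merits a correction because the correction is cheap and has to be in place before Day 1 samples are taken.

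**What to change.** **Collection.** In the Table 3-4 footnote and in Section 11.1 item 4, state that the Day 1 FE-1 sample is to be collected before the first dose, with home collection in the 24 hours before the visit allowed, and that later samples may be taken before or after dosing.

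**Baseline.** In Section 12.3.1, add an FE-1 rule: if no predose sample exists, a Day 1 sample taken after the first dose serves as baseline and is flagged, and a sensitivity summary leaves flagged values out.

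**Cost.** A sentence in each of the three places, with no added visit or sample. Some caregivers will have to bring a home sample to Day 1, and a child who passes no stool before dosing would be recorded as a minor deviation. The fallback keeps that child in the main FE-1 summaries.

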5 INTRODUCTION

5.1 Background

Cystic fibrosis (CF) is an autosomal recessive disease with serious, chronically debilitating morbidities and high premature mortality and at present, there is no cure. CF affects approximately 70,000 individuals worldwide,¹ with approximately 30,000 individuals in the United States (US),^{1,2} 32,000 individuals in the European Union (EU),³ 4,100 individuals in Canada,⁴ and 3,200 individuals in Australia.⁵ The incidence and prevalence of CF varies between racial groups. For example, CF is considerably more common in the Caucasian populations of North America and Europe than in Asian and African populations.^{2,3} Based on the size of the population, CF qualifies as an orphan disease.^{6,7} Despite progress in the treatment of CF with antibiotics and mucolytics, the predicted median age of survival for a person with CF is approximately 40 years.^{2,8,9} Although the disease affects multiple organs, progressive loss of lung function is the leading cause of mortality.¹⁰

Cystic fibrosis is caused by a defect in the gene encoding the cystic fibrosis transmembrane conductance regulator (CFTR), an epithelial chloride (Cl⁻) ion channel activated by cyclic AMP-dependent protein kinase A that is responsible for aiding in the regulation of salt and water absorption and secretion in various tissues. ¹¹ This function is defective in patients with CF due to a loss of either cell surface expression and/or function of CFTR.

More than 2000 mutations in the *CFTR* gene have been identified. ¹² The most prevalent mutation is an in-frame deletion in the *CFTR* gene resulting in a loss of phenylalanine at position 508 in the wild-type CFTR protein (F508del-CFTR). ¹³ The proportion of patients with CF who are homozygous for the *F508del-CFTR* mutation is similar across geographic regions: approximately 47% in the US², 44% in the EU³, 50% in Canada⁴, and 51% in Australia. ⁵ The *F508del-CFTR* mutation interferes with the ability of the CFTR protein to reach and remain at the cell surface, as well as to open and close, resulting in decreased Cl⁻ transport. ^{14,15} Because of the near-complete loss of CFTR chloride transport, the *F508del/F508del* mutation is typically associated with a severe form of CF, characterized by a rapid rate of lung function decline, colonization with *Pseudomonas aeruginosa*, a high incidence of pancreatic insufficiency, and reduced life expectancy. ^{16,17,18,19}

Based on the understanding of the molecular defects caused by *CFTR* mutations, 2 complementary approaches have been developed to address the decreased quantity and/or function of CFTR in order to enhance chloride transport in patients with CF. The first approach is to increase the quantity of CFTR delivered to the cell surface using small molecules known as CFTR correctors. The second approach is to increase the channel gating activity of CFTR at the cell surface using small molecules known as CFTR potentiators. One or both of these mechanisms may be necessary, depending on the specific mutation. Because the channel gating activity of CFTR delivered to the cell surface by CFTR correctors can be enhanced by CFTR potentiators, together, CFTR correctors and potentiators provide complementary therapeutic approaches to improve chloride transport.

Lumacaftor (LUM) is a CFTR corrector that improves the processing and trafficking of the F508del-CFTR protein, resulting in an increase in the quantity of F508del-CFTR protein at the cell surface. Ivacaftor (IVA) increases the channel open probability of the F508del-CFTR protein delivered to the cell surface by LUM, thereby enhancing total chloride transport. In the absence of LUM, there is very little F508del-CFTR protein at the cell surface for IVA to potentiate. The combined effect of LUM and IVA is increased quantity and function of F508del-CFTR at the cell surface.

LUM and IVA in combination is the first medicine designed to treat the underlying molecular defect and enhance the function of CFTR in patients homozygous for *F508del*. The LUM/IVA development program targets patients with CF who have the *F508del* mutation, the most common mutation in the *CFTR* gene.

Details about the LUM/IVA development program can be found in the Investigator's Brochure.²⁰

5.2 Study Rationale

CF greatly affects the pediatric population, as approximately half of the total CF population is less than 18 years of age. ²¹ Even before the widespread adoption of newborn screening, the majority of patients with CF were diagnosed in infancy or early childhood due to manifestations of the disease. Pancreatic destruction leading to pancreatic exocrine insufficiency begins in utero, and lung involvement is manifest by pulmonary inflammation and infection that begins shortly after birth. The present study is designed to obtain pharmacokinetic (PK) and safety information to support a proposed indication expansion of LUM/IVA in subjects 2 through 5 years of age, homozygous for *F508del*.

6 STUDY OBJECTIVES

6.1 Primary Objectives

Part A

To evaluate the PK of LUM and IVA and their respective metabolites in subjects aged 2 through 5 years with CF, homozygous for *F508del*

Part B

To evaluate the safety of LUM/IVA combination therapy in subjects aged 2 through 5 years with CF, homozygous for *F508del*

6.2 Secondary Objectives

Part A

To evaluate the safety of LUM/IVA combination therapy in subjects aged 2 through 5 years with CF, homozygous for F508del

Part B

• To evaluate the pharmacodynamics (PD) of LUM/IVA combination therapy in subjects aged 2 through 5 years with CF, homozygous for *F508del*

- To evaluate the off-drug PD response after the Washout Period
- To evaluate the PK of LUM and IVA and their respective metabolites in subjects aged 2 through 5 years with CF, homozygous for *F508del*

